1.1 Purpose of the Study

The overall objective of this study is to test the use of 4 weeks of 24 mg daily ondansetron as compared to placebo on symptoms and brain functioning in patients with obsessive-compulsive disorder (OCD) and tic disorders (TD). This is the second phase (R33 phase) of a 2-phase R21/R33 project. In the first (R21) phase, we found that single doses of 24-mg ondansetron significantly reduced activation of insula and sensorimotor brain regions in healthy volunteers.

Despite extensive research, 30-60% of OCD patients do not respond adequately to first-line treatments (1,2), with similarly disappointing rates in TD3. Treatment presents a particular challenge because these disorders are heterogeneous, with clusters of symptoms likely derived from differing neural etiologies. The Research Domain Criteria (RDoC) approach seeks to address this problem by investigating transdiagnostic components of behavior that more closely align with brain circuitry (4,5). This application focuses on sensory phenomena (SP) as a critical component of both OCD and TD with a discrete neural circuitry centered on the insula and somatosensory cortex. Consistent with the experimental therapeutic approach, the current project will test the ability of ondansetron, a 5-HT3 antagonist acting on sensory pathways, to engage this neural circuitry in order to modulate sensory phenomena.

Sensory phenomena are uncomfortable or aversive sensations that precede compulsions in OCD and tics in TD (6-10). They are highly prevalent, occurring in up to 70% of OCD patients (7-9) and 93% of TD patients (11,12). In the majority of cases, SP may actually drive the repetitive behavior (7,13,14) and are experienced as highly distressing (7,12,13,15), yet these symptoms are not well addressed by standard treatment approaches in OCD or TD (6,16-19). The current project will address this issue by investigating the novel use of ondansetron as a means to target neural systems underlying symptoms of SP. Much research points to a discrete circuit involved in detecting sensory information from the body, with activation of the insula and somatosensory cortex associated with the conscious perception of visceral and somatic sensation (20-25).

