2.1 Number, Gender, Age and Racial/Ethnic Origin of Subjects

2.1.1 Number

It is expected that approximately 45 participants will be enrolled at NYU Langone Medical Center in order to produce 30 eligible participants at this site. Approximately 45 participants will also be enrolled at Nathan Kline Institute to produce 30 evaluable participants at that site. Participants enrolled at NYU will primarily be recruited from flyers throughout the NYU campus, internet advertisements, newspaper advertisements, recruitment emails to university mailing lists and previous studies from prior studies conducted by the lab and will directly contact the Research Coordinator for more information.

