2.2 Inclusion Criteria

Criteria for all participants

- Ages between 18 and 60 years
- Fluent (speaking and writing) in English.
- Diagnosis of obsessive-compulsive disorder (OCD) or tic disorder (OCD) according to DSM-5 criteria as determined with the Mini International Neuropsychiatric Interview (MINI, Sheehan et al., 1998; J Clin Psychiatry, 59 Suppl 20, 22-33)
- Moderate or greater disorder severity: ≥ 16 on the Yale-Brown Obsessive Compulsive Scale (Y-BOCS) or ≥ 20 on the Yale Global Tic Severity Scale (YGTSS)
- Moderate or greater severity of sensory phenomena (≥ 6 on the Sensory Phenomena Scale, SPS)
- Stable on psychotropic medication for at least 6 weeks or unmedicated.

Additional criteria for all participants who are screened remotely

access to a computer or phone with a camera

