4. Picture Ratings and practice trials on task (10-30 minutes): Subjects will be asked to rate a series of 72 images. These images include 24 OCD images from the Berlin Obsessive-Compulsive Disorder Picture Set (Simon et al., 2012), as well as 24 threat-related and 24 neutral images. Threat-related images are from the standardized IAPS database and include pictures of snarling or ferocious looking animals, weapons, and injured or distressed-looking people. Neutral images are also taken from the IAPS database and include non-ferocious looking animals, people with neutral facial expressions, and objects such as books or tables. The images (OCD, threat and neutral) will be presented in random order. After viewing each image they will make two ratings: 1. how generally negative or positive the image makes them feel and 2. how much the image evokes their OCD symptoms. This task will be performed on REDCap if the visit is remote. Ratings made during this task will be used by the research team to pick images relevant to each subject's symptoms for the SP provocation task in the scanner (see below). Subjects may also be asked to perform practice trials of the fMRI tasks during the Experiment Visits.

The entire screening procedure is expected to take from 3-4 hours, depending on the pace of the subject in answering questions, the timeliness of the medical screen appointment, and whether practice trials for the task are performed. After the Screening Visit, if the subject is deemed safe and fit to participate in the study, they will be given the option to schedule an appointment for the Baseline Visit.

Study Group Assignment after Screening Visit:

After the Screening Visit, eligible subjects will be randomly assigned into two groups: one group will receive 24 mg of ondansetron and the other group will receive placebo daily for 4 weeks. Participants will receive a 40-day supply of drug at the Baseline Visit (Day 0) and instructed to take the first dose on the following day in the morning (Day 1). The 40-day supply includes a buffer so that participation in the trial is not disrupted in the rare case that a patient needs to reschedule the Mid-Trial or Final Visits at the last minute.

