- 3. SP provocation task: During the training session, the participant will rate images from the Berlin Obsessive-Compulsive Disorder Picture Set (Simon et al., 2012) on how much they evoke their OCD symptoms or not (tic disorder patients will also complete this task, but if they do not have OCD symptoms they will rate that none are evoked from the task stimuli). They will also rate threat-related images and neutral images from the based on

how negative they are or not. Threat-related images are from the standardized IAPS database and include pictures of snarling or ferocious looking animals, weapons, and injured or distressed-looking people. Neutral images are also taken from the IAPS database and include non-ferocious looking animals, people with neutral facial expressions, and objects such as books or tables. During the SP task in the scanner, patients view the OCD images that have been selected based on their ratings during the screening visit to trigger their OCD symptoms. Three different images of each type (SP, threat-related, neutral) are presented 6 times each in pseudorandom order over 2 runs. Each image is shown for 5 s, after which patients rate their current severity of SP on a 5-point scale ("none at all" to "very severe", 4 s), followed by a 2-6 s jittered ITI. Each run lasts approximately 4 min, for a total task time of 8 min.

There may be minor changes to the content or timing of these tasks and the scanning protocol as the experiment is prepared and in the early stages of implementation. Specifically, if problems are encountered along the way regarding the length of the protocol or the utility of the tasks (e.g., if the total length of the scanning session appears to be too long for subjects), we may remove or alter some tasks or scans to address these issues. In no case will the risks to the subjects be increased by any changes, and the total time of the scanning session will never be increased above 90 minutes.

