At the end of the visit, the patient will be given a "Journaling Sheet" where they will rate the severity of their OCD and sensory symptoms twice (afternoon and evening) during Week 1 (Days 1 to 7) and Week 4 (Days 21 to 28). The purpose of the sheet is to track any changes over the course of the day related to the time that they took the study drug.

(D and F) Phone Calls (Approximately Days 7 and 21, 30-60 minutes each call)

The experimenter will call the subject on the phone at pre-arranged times to ask about study compliance, evaluate any side effects patients might be experiencing, and assess symptoms. This will involve administering the Patient-Rated Inventory of Side Effects (PRISE), the Y-BOCS or YGTSS (for OCD and TD patients,

respectively), the SPS, and also assessing suicidal ideation in patients with QIDS item #12. During the Day 21 Phone Call session, the study team member will remind the subject to start filling out the Journaling Sheet. For patients with EKG at screening within the normal range but within 430-450 ms for men or 450-470 ms for women, we will have them come into the lab at NYU or NKI at week 1 (approximately 7 days) instead of doing a phone call to perform a surveillance EKG to determine continued safety to participate. If the visit is remote, participants will be transported to CTSI or OPRD using a car service paid for by the study in order to complete the EKG. They may also drive themselves. All other non-medical procedures listed for this visit will be conducted over the phone.

(E) Mid-Trial Visit (Approximately "Day 14", 2 hours)

For the Mid-Trial visit, the patient will meet with the study team remotely via Webex or come in-person to NYU or NKI to repeat symptom and side effects assessment (YBOCS/YGTSS, SPS, PRISE, and suicidal ideation) and fill out self-report questionnaires. In addition, the patient will meet with the licensed study team physician to ensure safety. This will be conducted in a separate, in-person visit if the first part of the visit is online. We will perform a repeat EKG during the mid-trial visit. The Mid-Trial Visit will ideally be scheduled for Day 14; realistically, we will allow patients to complete the procedures within a window of +/- 7 days. Participants will be transported to CTSI using a car service paid for by the study or using their own vehicles.

(F) Final (Exit) Visit (Approximately Day 28, 4-6 hours)

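### The objective covers OCD and tic disorders, but no stratification by diagnosis is described and the sensory-phenomena and brain comparisons have no diagnosis term or by-diagnosis estimate

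*Combined protocol and SAP*

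**What the plan says.** Section 1.1 states the objective as the effect of four weeks of ondansetron against placebo on "symptoms and brain functioning in patients with obsessive-compulsive disorder (OCD) and tic disorders (TD"). It gives a reason for studying the two together, namely "investigating transdiagnostic components of behavior that more closely align with brain circuitry". Section 2.2 admits either disorder: "Diagnosis of obsessive-compulsive disorder (OCD) or tic disorder (OCD) according to DSM-5 criteria" (the second abbreviation looks like a typing slip for TD). No quota, cap or expected mix is given. Section 2.1.1 plans about 45 enrolled at one site "in order to produce 30 eligible participants at this site", and the same numbers at the other.

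On allocation, section 4.1 says that "eligible subjects will be randomly assigned into two groups: one group will receive 24 mg of ondansetron and the other group will receive placebo". The dispensing pharmacy carries out the randomization for both sites. Ratio, blocking and stratification are not described.

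Section 4.2 tests ROI activation, resting-state connectivity and SPS change with two-sample t-tests of drug against placebo. A baseline covariate is added only if the groups differ at baseline. It also compares Y-BOCS and YGTSS changes between arms. By section 4.1 the Y-BOCS is given to OCD patients and the YGTSS to TD patients. A later paragraph of section 4.2 says that clinical or demographic differences found between the groups after randomization will be controlled for in all analyses. Its examples are age, gender, illness duration and medication dosage; diagnosis is not among them.

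**The concern.** Sensory phenomena and brain activation are the outcomes on which the trial's mechanism rests. For these outcomes the plan gives one number for the two disorders together. If that number is positive, the natural summary is that ondansetron acts in OCD and TD, although nothing in the analysis would show whether TD patients contributed. If it is null, an effect confined to one disorder could be diluted out of sight.

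There is some reason to think that diagnosis bears on the outcomes. In the picture provocation task, tic patients rate the OCD images too, but "if they do not have OCD symptoms they will rate that none are evoked from the task stimuli", so that contrast may not mean the same thing in both groups. This is one task of three; the blink-suppression task, the body-focused videos and the resting scan use no OCD pictures.

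Without stratification, the arms may also differ by chance in their share of TD patients. The adjustment rule depends on an observed difference and leaves open whether diagnosis counts.

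**Working it through.** **Inputs from the documents.** Target 30 + 30 = 60 patients (section 2.1.1); two arms (section 4.1); alpha 0.05 (section 4.2). The plan gives no effect size, SD or power, so 60 cannot be reproduced from a calculation; only the sum checks.

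**Assumptions.** 1:1 allocation (30 per arm), two-sided tests, a common SD, and a TD share that the documents do not state and that is varied here.

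**1. Can the pooled test be positive with no effect in TD?** Suppose the drug effect is 0.8 SD in OCD and 0 in TD, with TD balanced across arms. Pooled effect = 0.8 × OCD share. The pooled standard error is √(1/30 + 1/30) = 0.258 SD, and power comes from the noncentral t distribution with 58 degrees of freedom.

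| TD share | TD patients | Pooled effect | Noncentrality | Power |
|---|---|---|---|---|
| 0% | 0 | 0.80 SD | 0.80/0.258 = 3.10 | 86% |
| 10% | 6 | 0.9 × 0.8 = 0.72 SD | 0.72/0.258 = 2.79 | 78% |
| 20% | 12 | 0.8 × 0.8 = 0.64 SD | 0.64/0.258 = 2.48 | 68% |

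So it can, and with a modest TD share it would do so more often than not.

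**2. How uneven could the TD split be?** With 60 patients and 30 per arm, the number of TD patients in one arm is hypergeometric. Simple randomization (binomial) is shown for comparison.

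| TD patients | Split at least | 30:30 arms | Simple randomization |
|---|---|---|---|
| 10 | 7:3 | 0.299 | 0.34 |
| 15 | 10:5 | 0.233 | 0.30 |
| 20 | 13:7 | 0.170 | 0.26 |

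A 10:5 split gives TD shares of 10/30 and 5/30. The arm difference then shifts by 5/30 = 0.17 of the OCD–TD difference in mean change. If that difference were 0.5 SD (assumed), the shift would be 0.17 × 0.5 = 0.08 SD, about a third of the 0.26 SD standard error.

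**3. What could be said about TD alone?** With 15 TD patients split 8:7, the standard error is √(1/8 + 1/7) = 0.52 SD. The 95% half-width is 1.96 × 0.52 = 1.01 SD, or 2.16 × 0.52 = 1.12 SD with t on 13 degrees of freedom. For the drug-by-diagnosis difference, with the 45 OCD patients split 22:23, the standard error is √(1/8 + 1/7 + 1/22 + 1/23) = 0.60 SD and the half-width is 1.96 × 0.60 = 1.17 SD. These intervals describe; they do not test anything with useful power.

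**The case against.** Pooling is deliberate. The trial takes a transdiagnostic view, requires moderate sensory phenomena of every patient, and words Hypotheses 2 and 3a for the pooled population, with no claim for TD alone. This stands, and it justifies the pooled test as primary. It does not remove the need to look at diagnosis: a shared mechanism is the idea under study, and the drug-by-diagnosis estimate is the direct look at it.

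Chance imbalance is already allowed for in the error rate of a randomized comparison, and the shift in step 2 is small unless the disorders differ greatly in mean change. This also stands; imbalance is the lesser part of the point. The adjustment clause is open-ended and could be read to cover diagnosis. But it acts only on an observed difference, does not name diagnosis, and yields no estimate for either disorder.

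Three stronger readings are tempting, and the documents do not support them:

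- A reader might infer that no drug effect is planned within either diagnosis. The Y-BOCS and YGTSS comparisons are in effect just that, for overall severity, though the plan does not label them so.
- A reader might infer that the sample will be mainly OCD. Some advertising is OCD-oriented, but the health-record search in section 3.1 covers both diagnoses, and no mix is stated.
- A reader might infer that allocation is definitely unstratified. The plan is silent; the pharmacy's method is not described.

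**Conclusion.** The point holds as a gap in pre-specification, not as a flaw that invalidates the pooled test. For ROI activation, connectivity and SPS change, the plan has no diagnosis term, no estimate by diagnosis and no interaction, and it describes no stratification by diagnosis. The pooled result could not show that the finding extends to TD: with TD at 10% to 20% of 60 patients and no effect in TD, a 0.8 SD effect in OCD would still be detected with 78% to 68% power. A TD split of at least 7:3, 10:5 or 13:7 would occur in 30%, 23% or 17% of trials with 10, 15 or 20 TD patients. All these figures depend on the assumed mix, 1:1 allocation and a common SD. A powered claim for TD alone is out of reach at this sample size under any of these mixes.

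**What to change.** - Enter diagnosis as a pre-specified factor in the Hypothesis 2 and 3a models (ROI activation, connectivity, SPS change), whether or not the arms differ on it. State how patients with both disorders are classified.
- Report the drug–placebo difference with its interval for OCD and for TD, and the drug-by-diagnosis difference with its interval. Label these descriptive.
- Say that the confirmatory conclusion is for the pooled sensory-phenomena population as enrolled, and report the diagnosis mix.
- State the allocation ratio and method. If allocations remain and pack supply allows, have the pharmacy use separate blocked lists by diagnosis.

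The analysis changes can be written in at any time before unblinding. Diagnosis is already established at screening, so no patients or procedures are added. The cost is one degree of freedom in each primary model, one table and a more modest statement about TD. Separate lists would mean extra pack handling, since packs are ordered for 5 to 10 patients at a time subject to expiry. The documents do not say how many allocations remain, so that step is conditional.

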4.2 Data Analysis and Data Monitoring

(See R21/R33 application for section references)

The primary endpoints of the study are clinical symptoms and fMRI data. The specific analyses (independent and dependent variables) will be unique to each task, as described below. Safety and tolerability of 4 weeks of 24 mg ondansetron will also be evaluated.

Alpha level will be set at 0.05 for all analyses. Task-based fMRI analysis will focus on brain activation in an a priori ROI consisting of bilateral insula and somatosensory cortex, although exploratory whole-brain analyses will also be conducted. Primary group-level analyses for the R33 phase will be performed on a modified intent to treat sample consisting of participants completing at least 2 weeks of treatment. Missing data values are expected to amount to 10% or less of the data. We will consider them as MAR and impute based on a regression model. The degrees of freedom of t-tests will be adjusted appropriately. Secondary per-protocol analyses will also be conducted.

Task-based and symptoms analyses for R33:

First-level fMRI analysis: For each fMRI task, image analysis at the first (subject) level will specify separate regressors for baseline and week 4 for conditions of interest (e.g., for the "urges-for-action" task: blink suppression at baseline, blink suppression at week 4, rest at baseline, rest at week 4) to examine contrasts between baseline and week 4 (e.g., blink suppression vs. rest for baseline vs. week 4). For each task, contrasts will also examine activation during the baseline scan only (e.g., blink suppression vs. rest at baseline scan). These latter contrasts will be performed in order to measure and adjust for any baseline differences in ROI activation between ondansetron and placebo groups.

Group-level fMRI analysis: Testing for Hypothesis 2: Two-sample t-tests will compare ondansetron and placebo groups on change in activation over the 4-week trial (using first-level contrasts comparing baseline with week 4). However, if there are significant baseline differences between the groups within the insula and somatosensory ROI (using two-sample t-tests on baseline scan contrasts), standardized parameter estimates will be extracted from these regions for each subject. These parameter estimates will then be specified as covariates in follow-up one-way ANOVAs comparing ondansetron and placebo groups on change in activation from baseline to week 4 after adjusting for baseline differences.

Relationships with clinical symptoms: Testing for Hypothesis 3a: A change score will be computed between SPS score at baseline and after 4 weeks for each subject. Two-sample t-tests will compare ondansetron and placebo groups on SPS change scores to determine whether the intervention reduces SP significantly more than placebo. In addition, change scores from baseline to week 4 will be computed for measures of overall symptom severity (using Y-BOCS and YGTSS) and compared between ondansetron and placebo groups. If there are baseline differences between the groups in any of the symptom scales (SPS, Y-BOCS, or YGTSS), follow-up one-way ANOVAs will compare change scores between ondansetron and placebo groups after adjusting for baseline scores. Testing for Hypothesis 3b: If there are significant differences between ondansetron and placebo groups in (1) SPS change scores and (2) Y-BOCS or YGTSS change scores, a Sobel test of mediation 205, 206 will investigate whether group differences in Y-BOCS/YGTSS changes are mediated by SPS changes. Briefly, mediation analyses perform a series of regressions in order to determine whether the relationship between an independent and dependent variable (e.g., treatment group and Y-BOCS/YGTSS scores) reduces significantly after including a third mediator variable (e.g., SPS score). Testing for Hypothesis 3c: If there are significant differences between ondansetron and placebo groups in (1) SPS change scores and (2) change in ROI activation or connectivity from baseline to week 4, a Sobel test will investigate whether group differences in SPS change are mediated by changes in activation or connectivity.

Resting-state functional connectivity analysis: After heart rate and respiratory signals are removed from resting-"RETROICOR"207. analysis will proceed usina (www.nitrc.org/projects/conn) following our previous protocol26. Timecourses of the BOLD signal for each rest scan will be extracted from four seeds (6-mm radius spheres) in bilateral insula (two seeds in anterior and two seeds in mid-posterior insula, coordinates taken from prior work26,208). Partial correlations will be conducted between these timecourses and whole-brain gray matter, controlling for several factors. Timecourses from the top three principle components within white matter and CSF will be determined using the "CompCor" method209 and included as covariates to control for noise without having to regress out global signal210,211. Additionally, the inclusion of 12 motion variables (6 realignment parameters and first derivatives) as covariates will control for movement. Because movement is a major concern for connectivity analysis 212, we will exclude from restingstate analyses any subject moving > 1 mm or 0.5 degrees. Data will be filtered between 0.01 and 0.10 Hz213. At the first level, partial correlation coefficient images between each seed's timecourse and the whole brain will be z-transformed and compared in contrasts between baseline and week 4. For Hypotheses 2 and 3c (R33). two-sample t-tests will compare ondansetron and placebo groups in change in connectivity between baseline and week 4. As with task analyses, baseline differences will be probed using t-tests and included as covariates in follow-up ANOVAs if necessary.

Additional post-hoc analyses: Exploratory whole-brain analyses will be conducted for all contrasts of interest, correcting for multiple comparisons using cluster-level false discovery rate. For the R33 phase, we will probe for correlations between SPS score and whole-brain activation and connectivity in order to identify other future targets for treatment. We will also examine associations between other clinical measures (DOCS, PUTS, GAF)

and ondansetron treatment as well as brain functioning. Investigation of symptom trajectories over the duration of the trial will use ANOVAs with time (baseline, week 1, 2, 3, 4) as a repeated measure. Any clinical or demographic differences remaining between the groups after randomization including age, gender, illness duration, and medication dosage (using fluoxetine equivalence) will be statistically controlled for in all analyses. For illness duration and medication, follow-up analyses will investigate the relationship between these variables and study measures (brain functioning and symptoms), not only to control for confounding but also to interrogate these variables as factors of interest.

A Data Safety Monitoring Board consisting of external scientists was assembled in August of 2015 for the R21 phase. This DSMB met every 6 months (February, August of 2016, and March 2017) via teleconference to review aggregate safety data. The board will continue to meet at this same schedule during the R33 phase. The DSMB meeting in March 2017 approved continuation to the R33 phase using the procedures described in this protocol. The board last met on December 20, 2017 (6 months after the start of the R33 phase in June of 2017) and approved the continuation of the R33 phase.

- i. The primary safety measure discussed at DSMB meetings is the incidence of adverse events, which are assessed weekly throughout the trial using the Patient-Rated Inventory of Side effects (Rush et al., 2004, Control Clin Trials, 25, 119-142). The PRISE consists of a checklist of side effects in the categories of: Gastrointestinal, Heart, Skin, Nervous System, Eyes/Ears, Genital/Urinary, Sleep, Sexual Functioning, and Other (which includes symptoms related to energy and mood). Patients endorse items and indicate whether they are tolerable or distressing. Secondarily, safety outcomes related to results from medical surveillance tests (EKG, blood test) occurring during Mid-trial and Final visits will be discussed.
- ii. There are no predetermined stopping rules for the study. Every 6 months the DSMB will review side effects and determine whether the study may continue for the next 6 months. Critically, if any SAEs occur at any time during the trial, the study team will report this to the NYU Langone IRB and the DSMB within 48 hours and the determination regarding continuation of the study will be made at that time by both entities. In addition to the DSMB meetings, a study physician ([name]) will review side effects for each patient at the Mid-Trial and Final Visits. If there are any unexpected or severe side effects that the study physician determines pose a safety risk, this will be communicated immediately to the study team and the PI and a determination regarding continuation of the patient in the trial will be made.
- iii. Following the DSMB meetings, the Chair ([name], Yale University) discusses the safety data with the other board members, and together they make a determination about continuation of the study. This information is communicated both verbally to the PI (informally at the end of the teleconference), as well as in a written report prepared by the Chair and sent to the PI following the meeting.

In addition to safety data, the DSMB also reviews any proposed amendments to the study protocol, performs ongoing monitoring of drop-outs, determines whether study procedures should be changed or the study should be halted, and performs periodic review of the completeness and validity of data to be used for analysis of safety and efficacy. The DSMB also ensures subject privacy and research data confidentiality.

The Board comprises the following individuals:

[name], PhD

Associate Professor of Psychiatry and in the Child Study Center Director, Yale OCD Research Clinic Co-Director, Neuroscience Research Training Program Yale University

[name] is the Chair of the DSMB. He is an expert in neuroscience and obsessive-compulsive disorder. He has considerable experience in running clinical trials in OCD and related disorders, as well as conducting experimental studies in both animal and human subjects. [name] research and clinical work have been acknowledged by a number of prestigious awards, including grant funding from the National Institutes of Health,

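### The primary analysis set drops randomised patients who stop before 2 weeks, and no efficacy analysis of all randomised patients is named

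*Combined protocol and SAP*

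**What the plan says.** Section 4.2 names clinical symptoms and fMRI as the primary endpoints. The primary group-level analyses use a "modified intent to treat sample consisting of participants completing at least 2 weeks of treatment". The one other set is mentioned in a single sentence, "Secondary per-protocol analyses will also be conducted", without a definition. No analysis in Section 4.2 is said to include all randomised patients.

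On missing data, the section states: "Missing data values are expected to amount to 10% or less of the data". The method is: "We will consider them as MAR and impute based on a regression model". This comes after the sentence that restricts the set, and nothing says that imputation brings excluded patients back.

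Section 4.1 (Study Group Assignment after Screening Visit) places randomisation after screening. Study drug is handed out at the Baseline Visit (Day 0), with the first dose planned for the next day.

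For Hypothesis 3a, "A change score will be computed between SPS score at baseline and after 4 weeks for each subject", and the arms are compared with a two-sample t-test. The Y-BOCS and YGTSS comparison has the same form. Symptoms are also scored during treatment. The calls at about Days 7 and 21 include the SPS and "the Y-BOCS or YGTSS (for OCD and TD patients" respectively, and the Mid-Trial Visit at about Day 14 is to "repeat symptom and side effects assessment (YBOCS/YGTSS, SPS, PRISE, and suicidal ideation". These interim scores are used in "ANOVAs with time (baseline, week 1, 2, 3, 4) as a repeated measure", listed among the post-hoc analyses with no population stated. Scans are taken only at the Baseline and Final Visits.

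**The concern.** Randomisation makes the arms comparable at assignment. A set defined by staying on treatment for 2 weeks is formed later, and the two arms can be filtered differently. If, say, more patients stop early on ondansetron and they are the ones doing badly, the remaining ondansetron patients look better than the arm as randomised. The per-protocol set does not restore the comparison, since such sets are normally narrower still. A reader would have no planned efficacy result on all randomised patients with which to judge whether the exclusion mattered.

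The protocol does foresee stops that could fall in the first 2 weeks. Section 6.1 has patients discontinue if symptoms of serotonin syndrome appear. Section 4.1 adds a week-1 EKG for patients with borderline QTc. Section 6.6 anticipates early withdrawal.

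**Working it through.** **No stated figure to reproduce.** The plan gives no power calculation, dropout rate or allocation ratio. Section 2.1.1 plans 45 enrolled at each of two sites to yield 30, a loss of 1 − 30/45 = one third. It does not separate screening failures from later loss, so the number removed by the 2-week rule cannot be derived.

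**Step 1: inputs for an illustration.**
- From the documents: 2 × 30 = 60 patients (Section 2.1.1) and alpha 0.05 (Section 4.2).
- Assumed: 30 randomised per arm, two-sided testing, and no true effect. One arm has k = 1, 2 or 3 more early stoppers than the other, and they differ from those retained by 0.5 or 1.0 SD of the change score.

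**Step 2: shift in the estimate.** If a share k/30 of an arm is removed and differs by a gap from the rest, the retained mean moves away from the full-arm mean by (k/30) × gap. The standard error is √(2/30) = 0.258 SD, ignoring the few patients lost. Type I error comes from a noncentral t with 58 df and noncentrality shift/0.258.

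| k | gap (SD) | shift (SD) | type I error |
|---|---|---|---|
| 1 | 0.5 | 0.017 | 5.05% |
| 1 | 1.0 | 0.033 | 5.2% |
| 2 | 0.5 | 0.033 | 5.2% |
| 2 | 1.0 | 0.067 | 5.7% |
| 3 | 0.5 | 0.050 | 5.4% |
| 3 | 1.0 | 0.100 | 6.7% |

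The direction depends on which arm loses patients and whether they do better or worse.

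**Step 3: heavier assumed stopping.** In simulations with 30 per arm, stopping after a poor week-1 score, 5% stopping on placebo, and a week-1/week-4 correlation of 0.5 to 0.7:
- 10%, 15% and 20% stopping on ondansetron gave bias towards ondansetron of 0.04–0.07, 0.09–0.12 and 0.12–0.17 SD. Type I error was about 5–6%, 6–7% and 7–10%.
- Equal 5% stopping in both arms gave bias of about zero and type I error of about 5%.
- An all-randomised likelihood analysis using the week-1 scores stayed within 0.01 SD, with type I error of 4.2–4.9%, throughout.

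**Step 4: does a mixed model always help?** Bias in further simulations with assumed stop rates of up to 20% in one arm, in SD of a single score:

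| stopping driven by | 2-week set | mixed model |
|---|---|---|
| week-1 level or change | 0.004–0.073 | at most 0.004 |
| unseen week-4 change | 0.026–0.102 | 0.014–0.047 |
| unseen week-4 level | 0.028–0.066 | 0.037–0.092 |

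The mixed model removes the bias when stopping depends on scores already seen. It reduces the bias in the second case and is no better in the third.

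**Step 5: a separate gain.** The standard error of a baseline-adjusted contrast relative to a change-score contrast is √((1 + r)/2), where r is the baseline/week-4 correlation. For assumed r = 0.3, 0.5 and 0.7 this is 0.806, 0.866 and 0.922, a reduction of 19%, 13% and 8%. It comes from adjusting for baseline, not from including more patients.

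**The case against.** The strongest reply is that the effect is small and the evidence for it thin. That largely stands. Type I error of 7–10% needs 20% against 5% early stopping, a contrast found nowhere in the documents. Section 6.1 calls serotonin syndrome very unlikely. The week-1 EKG concerns only a borderline-QTc subgroup. The physician's side-effect review is tied to the Mid-Trial and Final Visits, so it precedes 2 weeks only through the visit window. The gastrointestinal dropout cited from an earlier study has no timing. A reader might infer that drug-related early stopping is expected and the primary result therefore materially biased. The documents show only that such stopping is possible.

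The base of 30 per arm is also uncertain. If evaluable at the second site means after losses, more patients are randomised, and the same k gives a smaller shift.

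A minimum-exposure set has a sensible rationale in a target-engagement study. That supports keeping it, but clinical symptoms are a primary endpoint and Hypothesis 3a is a comparison between randomised arms.

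Two stronger readings fail. One is that leaving the weekly scores out of the t-test is an error. The hypotheses are framed as baseline-to-week-4 change, the test matches them and is valid on complete data, and the imputation model could use the interim scores. The other is that the imputation inflates type I error. A figure of 6.6–7.5% at 10% missing needs single imputation without a residual and df reduced only in the reference distribution. If the reduced df also enters the variance it is about 5.4–6.0%, and multiple imputation gives 4.8–5.3%. Section 4.2 promises an appropriate df adjustment, so this is a specification detail.

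Nor can it be said that dropout goes unseen: the DSMB monitors drop-outs, and the trajectory ANOVA has no stated population. Neither is a planned efficacy analysis of all randomised patients.

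**Conclusion.** The point holds in this form: a stated rule makes the primary set depend on a post-randomisation event, and no named efficacy analysis keeps all randomised patients. That is certain from the text. The consequence is conditional: bias arises only if early stopping differs by arm, or relates differently to outcome in the two arms. On modest assumptions it is 0.02–0.10 SD against a standard error of 0.26 SD, in either direction. It should be fixed because the remedy is cheap, not because a large distortion has been shown. The unused weekly scores and the open imputation wording do not add to its severity.

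**What to change.** **Symptoms.** Make the primary analysis all randomised patients as assigned. Use a mixed model for repeated measures on the week 1 to 4 scores, with baseline as covariate, arm-by-week terms and the week-4 arm contrast as the test. Fit it separately for SPS, Y-BOCS and YGTSS. Keep the 2-week set as a minimum-exposure sensitivity analysis, and define the per-protocol set.

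**fMRI.** Include every randomised patient with both scans, whatever the time on treatment. Acknowledge that little can be recovered for those without a second scan.

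**Reporting and sensitivity.** Report by arm and reason the randomised patients excluded or without post-baseline data. Add a missing-not-at-random analysis, for example delta-adjusted, since the mixed model is not protected when stopping depends on unseen week-4 values. Where imputation is kept, state whether it is single or multiple and list its predictors.

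**Cost.** Plan wording and modest programming, settled before unblinding. No new visits are needed if only collected scores are used. The documents do not say whether assessments continue after a patient stops drug, and the plan should. The downsides are that the estimated effect may be somewhat diluted and that the mixed model still assumes MAR.
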